11.10 Safety Analysis

Safety evaluation will be conducted on the S population and using the same evaluation period as for efficacy analysis.

Safety will be evaluated based on reports of AEs either spontaneously reported or observed in clinical laboratory analyses. They will be coded according to the MedDRA.

Adverse events will be summarized based on number and percentages of subjects with any AEs, SAEs, and permanent withdrawal from the study. Adverse events will also be tabulated by SOC and preferred term.

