PSG and MWT are at the discretion of the PI and consent of the subject. Early withdrawal study subjects will be followed for a week after the last dose of study drug. All SAEs and nonserious AEs assessed by the PI as related to the study drug should be followed to resolution or until the PI assesses them to be chronic or stable.

It will be left to the investigator's clinical judgement whether or not an AE is of nature, or severity to require the subject's removal from treatment. A subject may also voluntarily withdraw from treatment due to what is perceived as an intolerable AE. If either of these occurs, the subjects must undergo an end-of-study assessment and receive appropriate care under medical supervision until symptoms cease or the condition becomes stable.

Withdrawal due to an AE should be distinguished from withdrawal due to lack of efficacy.

If the subject withdraws due to a SAE, the SAE must be reported in accordance with SAE reporting requirements.

Randomized subjects who have received at least 1 dose of study drug, who withdraw from the study prematurely will not be replaced.

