9.3.1 Period 4: Visit 9 (Week 15, Day 1) Follow-up

A safety follow-up visit will take place at Week 15 Day 1 (+4/-0) when subjects have been off study drug for ≥ 1 week. Study procedures include:

- Review and record all concomitant medication
- Safety assessment: To include assessment for residual effects of study drug and all AE review.
 - All AEs including residual effects of study drug to be reported as per study protocol requirements. The outcome of any AEs with a date of onset during the double-blind period should be reevaluated and any new AEs should be recorded. All SAEs and nonserious AEs assessed by the PI as related to the study drug should be followed to resolution or until the PI assesses them to be chronic or stable
 - In the event that a study subject is unable to return to clinic for the follow-up visit, telephone contact with the study subject to assess for AEs and or residual effects of study drug and concomitant medications is expected.
- Perform physical examination if determined clinically indicated by the PI
- Collect weight
- Collect vital signs (systolic and diastolic BP and heart rate) if clinically indicated
- Collect samples for hematology or biochemistry if clinically indicated, and perform urine pregnancy test (female subjects)

- Discuss off-study narcolepsy therapeutic pathway with study subject

9.4 **Unscheduled Visits**

Where additional study visits are clinically required an unscheduled visit will be performed. Where an unscheduled visit leads to the subject's withdrawal, the procedures to be performed are those planned for the EOS visit as detailed in [Section 9.2.6](#).

Study procedures include:

- Compliance with drug washout requirements
- Confirmation of continued eligibility
- Assess study restrictions compliance: (i) abstinence from alcohol, (ii) smoking restrictions, and (iii) all other study restrictions
- Assess drug abuse and dependence. Clinical judgement to be exercised in determining need for performing urine drug screen for benzodiazepines, cannabis, cocaine, opiates and barbiturates
- Assess compliance with drug handling, management and safety requirements.
 - Confirm subject is adhering to requirement to eat at least 2 hours before taking study drug
 - Subject re-education on study drug safety and handling and study-related procedures if deemed necessary by site PI
- Review and record of concomitant medication
 - Assess for adherence to prohibited medication requirements
- Document any AEs

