If the investigator determines that the causality is unknown, the PI must then assign a causality of "Possibly" for the purposes of reporting. The causality must be clearly documented in the subject's medical notes and eCRF and report in accordance with the SAE reporting requirements if applicable.

Action Taken

The investigator will describe the action taken in the appropriate section of the eCRF, as follows:

- None
- Study drug stopped
- Study drug temporarily interrupted
- Concomitant medication
- Other, specify.

Adverse Event Outcome

The investigator will assess the outcome of the AE or SAE as follows:

- Fatal (the subject has died)
- Resolved (the AE or SAE has ended)
- Ongoing (the AE has not ended)*
- Unknown (lost to follow-up after repeated unsuccessful attempts to contact the subject)

* An AE outcome can only be categorized as ongoing if the AE is:

- Ongoing at the end of the reporting period: improved, stable or worsening
- Ongoing: improved, stable, or worsening, and referred to the subject's physician or a specialist.

Follow-up of Adverse Events

All investigators should follow up subjects with AEs until the event is resolved or until, in the opinion of the investigator, the event is stabilized or determined to be chronic. Details of AE resolution must be documented in the eCRF.

Subjects should be followed for 7 days after receiving the last dose of study drug, and any AEs that occur during this time should be reported according to the procedures outlined above.

Documentation and Reporting of Adverse Events

Attention will be paid to the occurrence of AEs at all stages of the clinical study starting from signing of the informed consent to the follow-up visit which takes place 1 week after study completion or 1 week after premature withdrawal. Baseline events (i.e. medical history events that are ongoing) captured at the first study visit will only be recorded as AEs if during the screening and assessment period or double-blind period there is deterioration.

Information regarding all AEs, including SAEs, will be collected at each visit. All AE/SAEs that are encountered during the protocol specified AE/SAE reporting period will be followed to their resolutions, until the investigator assesses them as stable, or the subject is lost to follow-up.

Adverse events will be identified as treatment-emergent (TEAE) if the event occurs or increases in severity after the first dose of study drug is taken.

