11.3.2.1 Safety (S) Population

The S population includes all subjects that receive at least one dose of study drug. Subjects will be assigned to treatment arms based on the treatment actually administered (FT218 if active drug was administered at any time, placebo otherwise).

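### Protocol 11.10 ties safety to an undated efficacy period, which conflicts with the first-dose TEAE rule and post-dose AE reporting; the SAP display groups give Week 1 and post-treatment events no place

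*Protocol*

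**What the plan says.** Protocol 11.10 sets the safety window by reference to efficacy: "Safety evaluation will be conducted on the S population and using the same evaluation period as for efficacy analysis". It then names the counts to be produced: "Adverse events will be summarized based on number and percentages of subjects with any AEs, SAEs, and permanent withdrawal from the study".

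Other sections set a wider scope:

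- Protocol 10.1.2.1 calls an AE treatment-emergent "if the event occurs or increases in severity after the first dose of study drug is taken". SAP 4.7 uses the same start. Neither gives an end.
- Protocol 11.3.2.1: "The S population includes all subjects that receive at least one dose of study drug". SAP 3.3 agrees.
- Protocol 10.1.2.1 has AEs watched for "starting from signing of the informed consent to the follow-up visit", and "Subjects should be followed for 7 days after receiving the last dose of study drug, and any AEs that occur during this time" are to be reported. At Visit 9, Protocol 9.3.1 adds that "any new AEs should be recorded". For those who stop early, Protocol 8.3.4 says: "Early withdrawal study subjects will be followed for a week after the last dose of study drug".
- SAP 2.6.3 tabulates every AE and SAE by MedDRA class and term, with no period limit.

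For by-dose display, SAP 4.1.5 lists six groups: 9 g, 7.5 g and 6 g, each with its concurrent placebo. The 6 g group is labelled Period 3a, weeks 2-3. SAP 4.7 allocates each AE to the study period in which it began.

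**The concern.** The sentence in 11.10 is a stated rule, not an omission. Taken at its word, it restricts safety to a period chosen for efficacy contrasts, and no statistics section dates that period. Some treatment-emergent events that the protocol requires sites to record could then be left out of the AE tables. On the narrowest reading, a subject who takes study drug only in Week 1 stays in the Safety denominator but has no dosing day inside the window, so an AE that begins in Week 1 adds nothing to the AE count. The week after the last dose, when Visit 9 looks for residual effects, would also be outside for completers. A programmer working from Protocol 11.10 and one working from SAP 2.6.3 and 4.7 could produce different AE tables.

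The display groups raise a second, smaller problem. Week 1 is dosed at 4.5 g and belongs to Period 3a, but none of the six groups is for 4.5 g or for post-treatment time.

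**Working it through.** **Inputs.** Dose durations are 1 week at 4.5 g, 2 at 6 g, 5 at 7.5 g and 5 at 9 g (SAP 2). The last dose is on Week 13 Day 7 (SAP 4.1.4). AEs are reported for 7 days after that. Visit 9 is on Week 15 Day 1, +4/-0 days (Protocol 9.3.1). The SAP contrast windows are weeks 2-3, 4-8 and 9-13 (SAP 4.1.3).

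**The plan's own figure.** Protocol 6.5 describes a 12-week evaluation of efficacy and safety within 13 weeks on drug. 2 + 5 + 5 = 12 and 12 + 1 = 13, so it reproduces, and the 12 weeks match weeks 2-13. That text is rationale, not a definition in the statistics section.

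**Calendar.** First dose is Day 1. Last dose is 13 × 7 = Day 91. Last dose plus 7 is Day 98. Visit 9 is 14 × 7 + 1 = Day 99, up to Day 103.

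**Three readings of the efficacy period, for a completer followed 98 days:**

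| Reading | Source | Days inside | Days outside |
|---|---|---|---|
| A: SAP windows, weeks 2-13 | SAP 4.1.3, 4.1.5; compare Protocol 6.5 | 8-91 (84) | 98 - 84 = 14; 14/98 = 14.3% (7 in Week 1, 7 post-dose) |
| B: Periods 3a to 3c(ii) | Protocol 11.9.1.2; SAP 4.6.2; Period 3a as weeks 1-3 in SAP 2.3 | 1-91 (91) | 98 - 91 = 7; 7/98 = 7.1% (post-dose only) |
| C: all of Period 3, through Week 14 | SAP Table 1, Period 3c(iii) | 1-98 (98) | 0/98 |

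On reading C, only the days up to Visit 9 remain outside: 1/99 = 1.0% to 5/103 = 4.9%. Protocol 11.9.1.1 and SAP 4.6.1 add that model time covers all observations, again without dates. Protocol 11.10 does not say which reading applies.

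**How exact the shares are.** The 9 g MWT is done on Week 14 Day 1, which is 13 × 7 + 1 = Day 92. Taken to the day, readings A and B would exclude a co-primary 9 g measurement. The windows are therefore not strict day limits, and 14.3% and 7.1% only illustrate scale.

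**Laboratory data.** Protocol 11.10.1.1 and SAP 4.7 admit anyone with a baseline value and a test after first dose. That rule has no efficacy-period limit either.

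**Display groups.** Protocol 9.2.1, Protocol Appendix 17.2 and SAP 2.3 all place Week 1 in Period 3a, so 7 of its 21 nights (33%) are at 4.5 g. Allocated by period of onset, a Week 1 AE belongs to Period 3a and could appear under 6 g. Allocated by the weeks in the label, it has no group. An AE on Days 92-98 has no group either.

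**The case against.** The strongest reply is that the SAP already covers these events. Protocol 11.1 leaves detail to the SAP. SAP 2.6.3 tabulates all AEs and SAEs, SAP 4.7 counts from first dose, and SAP 3.3 needs only one dose. Events are lost only if 11.10 is followed against the SAP and a restrictive reading is chosen. Reading A also borrows windows that SAP 4.1.3 wrote for dose-against-placebo comparisons. All of this stands and limits the consequence. It does not remove a protocol sentence that says something different.

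On display, the 6 g label can be read as the weeks 2-3 part of Period 3a, so that nothing is mislabelled. That is fair, but on that reading Week 1 has no by-dose group. The SAP safety objective names only 6, 7.5 and 9 g, whereas Protocol 7.3 concerns FT218 as a whole. Protocol 11.4.1 plans by-arm summaries, where a Week 1 event fits, although SAP 4.1 words the rule by dose group. Table layouts may lie in the redacted text after SAP 4.7.

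A reader might infer three stronger things that the documents do not support:

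- That Week 1 withdrawals for AEs would go uncounted in the report. Protocol 11.5 and SAP 4.2 summarise when and why subjects withdrew, by period and overall; SAP 4.2 lists adverse event as a reason. SAP 4.1.5 has the listings show all eCRF data.
- That SAP 1.2 declares no departure from the protocol. It says only that the item is not applicable.
- That the choice of window would be made after unblinding. The first-dose rule and the all-AE tabulation are already written into the SAP, and the data stay blinded until after database lock.

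**Conclusion.** The sentence in Protocol 11.10 is wrong as written. It ties safety to an undated efficacy period and contradicts the protocol's own TEAE rule, Safety set and post-dose reporting, as well as SAP 2.6.3. On two of the three available readings, required AE reporting time falls outside the AE tables: about 14% of a completer's 98 days on reading A and about 7% on reading B. On reading C essentially none does. These shares assume full-length dosing and visits on schedule. They do not measure lost events, since the documents give no AE rates. Only tabulation is at issue, because AE collection, SAE reporting, listings and disposition counts do not depend on the sentence.

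The display point holds in limited form. In by-dose tables built on the six groups shown, a Week 1 AE has no group or could appear under 6 g, and a post-treatment AE has none. This is subject to the redacted layouts and the by-arm summary. Both points should be corrected; neither affects the efficacy analysis.

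**What to change.** 1. Replace the sentence in Protocol 11.10 with: *All TEAEs from first dose through the follow-up visit (at least 7 days after last dose) will be tabulated on the Safety population.* State the same end in SAP 4.7, which now gives none.
2. In by-dose safety tables, show Week 1 (4.5 g with concurrent placebo) and post-treatment onset as separate groups, next to the by-arm summary in Protocol 11.4.1, unless the redacted layouts already do so.

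The cost is one protocol sentence, a few words in SAP 4.7 and 4.1.5, and a few table columns. No new data are needed, and the efficacy analysis does not change.

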11.10.1.1 Laboratory Data

Laboratory data will be summarized in terms of the proportions of subjects with clinically relevant abnormalities using normal ranges. Shift tables will tabulate baseline to most extreme post baseline value. Summary statistics of raw data and change from baseline values, including means, medians, standard deviations, and ranges will be produced. Analyses will include all subjects in the S population who have had at least one laboratory test performed after the first study drug administration with an available baseline laboratory value. Baseline values will be measured as the last available measure before taking study drug.

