15. Female subjects who are lactating or have a positive pregnancy test. Females of reproductive potential not willing or able to employ effective methods of birth control/contraception to prevent pregnancy for the duration of the study and for up to 1 week after completing study treatment
16. Any current malignancy and/or any history of malignancy within last 3 years
17. A history of seizure disorder, head trauma, or past invasive intracranial surgery
18. Subjects with severe chronic obstructive pulmonary disease. Subjects with mild to moderate chronic obstructive pulmonary disease and assessed as stable by the principal investigator (PI) are eligible

19. Principal investigator judgement on other underlying respiratory and/or other underlying condition or disorder that would potentiate risk of respiratory or CNS depression with concomitant use of sodium oxybate
20. Known hepatitis B surface antigen-positive status or known or suspected active hepatitis C infection
21. Known human immunodeficiency virus infection or acquired immunodeficiency syndrome related illness
22. Scheduled for procedures requiring general anesthesia during the study
23. Known contraindication/allergy/sensitivity/intolerance to the study drug, sodium oxybate, or the inactive ingredients of FT218 or placebo
24. Atrial fibrillation or an abnormal electrocardiogram (ECG) demonstrating clinically significant dysrhythmia(s)
25. Recent myocardial infarction or coronary revascularization (less than 3 months)
26. Uncontrolled hypertension
27. Known succinic semi-aldehyde dehydrogenase deficiency
28. Moderately or severely altered blood chemistry as defined by any one of the following:
 - a. A Cockcroft-Gault calculated creatinine clearance < 60 mL/min; OR
 - b. Liver function tests more than twice the upper limit of normal; OR
 - c. Serum bilirubin more than 1.5 times the upper limit of normal

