10.1.2.2 Clinical Laboratory Evaluation

The hematology and biochemistry laboratory analyses will be performed at a central laboratory (ACM Global Central Laboratory, Rochester, US). Reference ranges will be supplied and used by the investigator to assess the laboratory data for clinical significance and pathological changes. The following laboratory safety tests will be performed:

Hematology

Hemoglobin, hematocrit, white blood cell count (total and differential), red blood cell count, platelet count, mean cell volume, mean cell hemoglobin, and mean cell hemoglobin concentration

Biochemistry

Creatinine, blood urea nitrogen, aspartate transferase, alanine transferase, gamma glutamyltransferase, alkaline phosphatase, total bilirubin, albumin, globulin, total protein, sodium, potassium, chloride, bicarbonate, estimated glomerular filtration rate, carbon dioxide, glucose, total cholesterol, triglycerides, and creatine phosphokinase.

Urinalysis

pH, glucose, ketones, blood, and protein by dipstick test at the central laboratory. If any of these parameters gives a positive result, a quantitative result will be transmitted.

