4.7 SAFETY ANALYSES

Safety evaluations will be performed on the safety population using the actual treatment administered.

Adverse events will be identified as treatment-emergent (TEAE) if the event occurs or increases in severity after the first dose of study medication is taken. Adverse events will be identified as mild, moderate or severe and related to the treatment as reported on the CRF. The adverse events will be assigned a preferred term (PT) and a system organ class (SOC) according to the Medical Dictionary for Regulatory Activities (MedDRA), latest version. In counting the number of events reported, a continuous event, i.e., an event reported more than once and which did not cease, will be counted only once with the worst recorded severity. Non-continuous AEs reported multiple times by the same subject will be counted as multiple events. AEs will be assigned to the period of the study corresponding to the time of onset. Events presenting immediately prior to the first dose of study medication that do not worsen in severity, will not be included. In deriving the tabulation relating to preferred term reporting, the severity of a recurrent AE will be taken to be the most severe and the relationship to study medication as the most probable within the relevant period of the study. Total exposure to FT218 will be determined in terms of number of days and dose.

Laboratory data will be summarized in terms of the proportions of patients with clinically notable abnormalities using normal ranges. Shift tables will tabulate baseline to most extreme post baseline values. Summary statistics of raw data and change from baseline values will be obtained including means, medians, standard deviations and ranges will be produced.

The summaries will include subjects in the safety population who have had at least one laboratory test performed after the first study drug administration with an available baseline laboratory value. Baseline values will be measured as the last available measure before taking study drug.

[REDACTED]

[REDACTED]

[REDACTED]

[REDACTED]

[REDACTED]

[REDACTED]

[REDACTED]

[REDACTED]

[REDACTED]

[REDACTED]

[REDACTED]

[REDACTED]

[REDACTED]

[REDACTED]

[REDACTED]

[REDACTED]

[REDACTED]

[REDACTED]

[REDACTED]

[REDACTED]

[REDACTED]

[REDACTED]	[REDACTED]	[REDACTED]
[REDACTED]	[REDACTED]	[REDACTED]
[REDACTED]	[REDACTED]	[REDACTED]
[REDACTED]	[REDACTED]	[REDACTED]
[REDACTED]	[REDACTED]	[REDACTED]
[REDACTED]	[REDACTED]	[REDACTED]

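### Laboratory abnormalities called clinically relevant are defined by normal ranges alone and need not be new, so for liver tests and bilirubin the proportion counts values permitted at entry

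*Protocol*

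**What the plan says.** Protocol 11.10.1.1 reports "proportions of subjects with clinically relevant abnormalities using normal ranges". SAP 4.7 reports "proportions of patients with clinically notable abnormalities using normal ranges". The normal range is the only criterion visible in either place, and neither says that the value must have been normal at baseline. The Protocol takes Safety-population subjects with at least one test after first dose and "with an available baseline laboratory value"; the SAP does the same.

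Both sections also plan baseline-adjusted outputs. In the Protocol's words: "Shift tables will tabulate baseline to most extreme post baseline value", and "Summary statistics of raw data and change from baseline values, including means, medians, standard deviations, and ranges will be produced". The shift categories are not given.

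Protocol 8.3.3, exclusion 28, sets the entry limits. A subject is excluded for "Liver function tests more than twice the upper limit of normal; OR" or for "Serum bilirubin more than 1.5 times the upper limit of normal", or for a Cockcroft-Gault creatinine clearance below 60 mL/min. Its heading describes values beyond these limits as moderate or severe alterations.

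Protocol 10.1.2.2 adds: "Reference ranges will be supplied and used by the investigator to assess the laboratory data for clinical significance and pathological changes".

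**The concern.** The protocol uses two yardsticks for the same analytes. At entry, a liver test between 1 and 2 times ULN, or bilirubin between 1 and 1.5 times ULN, is acceptable. On treatment, the same value in the same subject is labelled clinically relevant.

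The proportion therefore mixes values brought into the trial, values just outside the range by chance, and new elevations. A reader of the report would take the label at face value in both arms, and a small excess of new or marked elevations on FT218 would be harder to see. Hematology and biochemistry are scheduled only once on treatment (Protocol 9.2.6, Visit 8). The follow-up draw at Visit 9 is taken only if clinically indicated. With essentially one value per subject, much depends on how an abnormality is defined.

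**Working it through.** The plan states no laboratory rate or threshold, so there is no figure to reproduce. The check has two parts: what each rule does with individual subjects, and an illustration of the dilution.

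**1. Individual subjects (ALT in multiples of ULN)**

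| Baseline to on-treatment | Normal-range rule | Shift table, if low/normal/high | New and >2x ULN |
|---|---|---|---|
| 1.8, unchanged | counted | high to high | not counted |
| 1.8, falling but still above 1 | counted | high to high | not counted |
| 1.9 to 5 | counted | high to high | counted |
| normal to 1.1 | counted | normal to high | not counted |
| normal to 5 | counted | normal to high | counted |

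The normal-range rule treats all five alike. A low/normal/high shift table separates new from pre-existing elevations. It does not separate 1.1 from 5, or an unchanged 1.8 from a rise from 1.9 to 5.

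**2. Dilution for a single analyte, upper limit only**

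Assumptions, none of them in the documents:
- the range covers the central 95% of healthy values, so the chance rate above ULN is c = 0.025;
- a fraction q of subjects is above ULN at baseline and stays there;
- the drug produces a new elevation in s = 0.05 of subjects.

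Formulas:
- Placebo proportion = q + (1 − q)c
- FT218 proportion = q + (1 − q)[1 − (1 − c)(1 − s)], where 1 − 0.975 × 0.95 = 0.07375
- Difference = (1 − q)(0.07375 − 0.025) = (1 − q) × 0.04875
- Share of placebo flags already present at entry = q / placebo proportion

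| q | Placebo | FT218 | Difference (points) | Ratio | Placebo flags present at entry |
|---|---|---|---|---|---|
| 2% | 4.45% | 9.2% | 4.8 | 2.1 | 45% |
| 5% | 7.4% | 12.0% | 4.6 | 1.6 | 68% |
| 10% | 12.25% | 16.6% | 4.4 | 1.4 | 82% |
| 15% | 17.1% | 21.3% | 4.1 | 1.2 | 88% |
| Baseline-normal subjects only | 2.5% | 7.4% | 4.9 | 2.95 | none |

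The absolute difference shrinks only by the factor 1 − q. The ratio falls much faster, and the noise rises. At q = 10%, with n randomised per arm:
- Standard error of the crude difference: √(0.1225 × 0.8775 + 0.1664 × 0.8336)/√n = 0.496/√n
- Standard error among baseline-normal subjects (0.9n per arm): √[(0.025 × 0.975 + 0.07375 × 0.92625)/0.9]/√n = 0.321/√n
- Ratio: 0.496/0.321 = 1.55, whatever the arm size

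The crude proportion thus shows a slightly smaller difference with about one and a half times the standard error. Further rises in subjects already above ULN add nothing to the count, so they are lost altogether.

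**The case against.** The strongest reply is that the same paragraphs already deal with baseline. They require a baseline value and plan shift tables, change-from-baseline statistics and raw-value ranges, all in a placebo-controlled trial. A stable entry value would not appear as a new abnormality in a shift table. This stands, and it limits the point. The gap that remains is grading: the categories are unstated, means average over a few marked values, and a range shows the largest value but not how many subjects had one.

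Second, Protocol 10.1.2.2 has investigators use the ranges to judge clinical significance. Abnormal test findings can also be adverse events, which must begin or worsen after first dose to be treatment-emergent. So a clinically judged route exists. Neither summary rule, however, says that this judgement enters the proportion.

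Third, exclusion 28 sets eligibility limits, not analysis thresholds, so the two uses do not formally contradict each other. That is correct. The limits are simply ones the protocol already states. The entry-limit argument also covers only liver tests and bilirubin, not the whole panel.

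Fourth, a fixed threshold alone would miss modest rises, such as normal to 1.5 times ULN. This is why the normal-range shift tables should stay.

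Finally, SAP text after 4.7 is redacted, so further criteria cannot be ruled out. If they exist, the visible rule should point to them.

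**Conclusion.** The point holds as a defect of definition and labelling in one descriptive proportion. For liver tests and bilirubin, the stated rule counts values that the protocol permits at entry. This dilutes the contrast between arms and attaches the label clinically relevant to unchanged values. The shift tables recover part of the information, but not all of it if their categories are low/normal/high. The size depends on how many subjects enter above ULN, which the documents do not give. The 2% to 15% range, the 5% effect and the 2.5% chance rate above are assumptions.

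A reader might infer more than this, and three stronger readings are not supported:
- **That pre-existing and chance values overwhelm real drug signals.** No figure in the documents shows this, and the baseline-adjusted summaries and the placebo arm count against it. Randomisation makes the effect noise, not bias.
- **That most subjects would be flagged by chance, because many analytes are measured.** This would apply to a count of any abnormality across the panel, and no such composite is planned. Under the 95% assumption, a single analyte has a chance rate of about 2.5% per tail.
- **That a laboratory test would lose significance.** The laboratory sections plan summaries and describe no hypothesis test.

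The change is worth making because it is cheap. It does not affect the efficacy conclusions.

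**What to change.** Before unblinding, amend Protocol 11.10.1.1 and SAP 4.7 as follows:

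1. Define the reported proportion as treatment-emergent (criterion not met at baseline, met after first dose) and beyond a fixed threshold.
2. Use the limits already in exclusion 28 as reporting thresholds: liver tests >2x ULN, bilirubin >1.5x ULN, and creatinine clearance <60 mL/min. Name the analytes that count as liver tests. Clearance has to be calculated from creatinine, because 10.1.2.2 lists creatinine and estimated glomerular filtration rate but not clearance.
3. Fix thresholds for the remaining analytes at the same time.
4. Use one term in both documents, and say whether investigator judgement enters the proportion.
5. Keep the normal-range shift tables, but state categories that separate grades above ULN, so that a rise from 1.9 to 5 times ULN is visible.

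The cost is wording in two documents, one reprogrammed descriptive table, and agreement on limits for the other analytes. It needs no new data and no extra visits. These are reporting thresholds only, and clinical management does not change.
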